Aims/Hypotheses	
Specific Aim 1 - (PRIMARY): Compare the incidence of admission to the NICU in 35⁰-41⁶ week GA non-vigorous newborns receiving Umbilical Cord Milking (UCM) to those receiving Early Cord Clamping (ECC).
 
H1: Compared to ECC subjects, UCM subjects will have a decreased incidence of NICU admission (based on predefined criteria).
 
Specific Aim 2 (SECONDARY): Compare the safety and efficacy profiles in 35⁰-41⁶ week GA non-vigorous newborns receiving UCM to those receiving ECC. Compared to ECC subjects, UCM infants will have:
 
H2: Higher cerebral oxygen saturations in the first 10 minutes of life (sub-study at two (2) sites, n=20).
 
H3: Receive a greater placental transfusion as estimated by hemoglobin levels by 48 hours of life and better blood pressure; will not have increased rates of hyperbilirubinemia compared to ECC subjects; will have decreased resuscitation interventions, level of HIE, use of therapeutic hypothermia, use of volume expanders, and length of hospitalization.
 
H4: Will have improved developmental outcome scores on the Ages & Stages Questionnaire, Third Edition (ASQ-3); UCM subjects will have a lower rate of medium to high risk scores on the MCHAT at 2 years of age.
 
H5: Better cardiac function as measured by echocardiography at 12 hours of life (sub-study at two (2) sites, n=200).

Design and Sample Size	This prospective multi-national cluster randomized crossover (CRXO) trial randomizes by hospital wherein each institution is randomized over time to each arm of the study n=1200 infants – 600 UCM/600 ECC
Inclusion Criteria	
 Non-vigorous newborns born between 35⁰-41⁶ weeks gestation
Exclusion Criteria	
 Known major congenital or chromosomal anomalies of newborn Known cardiac defects other than small ASD, VSD and PDA Complete placental abruption/cutting through the placenta at time of delivery Mono-chorionic multiples Cord anomaly (i.e. avulsion or true knot) Presence of non-reducible nuchal cord Perinatal providers unaware of the protocol Incomplete delivery data Infants born in extremis, for whom additional treatment will not be offered

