As this is a cluster randomized crossover trial where the standard of care for every non-vigorous infant will be the same over a year at each site it is unlikely there will be a significant portion of newborns that will receive the wrong allocation based on the cluster. The inclusion/exclusion criteria were designed to be minimal and pragmatic for providers to decide readily if the infant should receive the treatment arm. The outcomes for infants with protocol violations will be measured and analyzed according to original allocation by intention-to-treat principles. Only newborns who meet pre-defined exclusion criteria (i.e. cord avulsion or congenital anomaly) will be excluded from the primary analyses, although we will verify that there is not a differential occurrence by treatment from procedure. This strategy was successful in our previous trials.

In prior cord milking trials conducted by [name], protocol violation rates for UCM (milking <4 times) were <5 percent. To ensure optimum compliance, he conducted extensive education and certification of our obstetricians in the delivery room. For the proposed trial, the site investigators all have significant experience with UCM and have equipoise of both cord management techniques. All lead perinatal investigators agreed on the techniques and will ensure their colleagues are adequately trained on the maneuvers to minimize site variability. Sites also agreed on institutional policies to video record the UCM techniques at initial startup to minimize site-to-site and inter-observer variations. Videos will be kept at local sites and used solely for study specific training purposes. Videos will be kept secure per local institutional policies. Site PIs will be considered 'certified' upon agreement of the lead site PI (AK). Training videos and materials will be disseminated to be used as a refresher for delivery room staff, fellows, and attending neonatologists. Monthly teleconference meetings will be conducted to examine site comfort with, and performance of UCM techniques, as well as record keeping, and other study or regulatory issues.

V. STATISTICS

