Sample size and power calculation We estimated that a sample size of 1200 across ten sites would be needed to test efficacy of UMC versus ECC for the primary outcome. This was based on the following assumptions: a clinically meaningful 35% reduction in NICU admissions (16.25% for UCM versus 25% for ECC), a two-sided type I error alpha = 0.05, 85% power, 0.02 rho (within cluster within period correlation), 0.02 eta (within cluster between period correlation), and a correction factor (4 x cluster size) for the small number of clusters(51).

For the longer-term neurodevelopment outcome scores, we estimated that a sample size of 1200 across ten sites, with an assumed two-sided type I error alpha = 0.05, 0.02 rho, 0.02 eta, a correction factor (4 x cluster size) for the small number of clusters, and Cohen's d = 0.25, power ranges from 79% to 87% when assuming a range in lost to follow-up from 20% to 10%. The original sample size for this trial was 1000. However, at the first DSMB meeting in May 2019 only four sites had begun enrollment and enrollment was nearing completion of the crossover point (nearly 2/3 complete in the first arm), and two sites were unable to obtain IRB approval. Therefore in conjunction with the DSMB, the decision was made to reassess the sample size calculation for ten sites.

Feasibility Based on the numbers of newborns at each of ten sites, we expect a total of approximately 1500 newborns with a 1-minute Apgar of ≤ 3 per year. Estimating conservatively that at least 50% will be classified as non-vigorous, a 2-year period of recruitment would be required. The ten sites agree to recruit and each one has provided an estimated number 35-41+6 weeks infants delivered per year.

Statistical Approaches for Testing Hypotheses

All statistical analyses will be based upon the total cohort of patients randomized into the trial. Patients will be included in the treatment group to which they were randomly assigned. We will use the intent-to-treat analysis to determine treatment difference between the UCM and ECC groups.

Descriptive statistics (counts and proportions for categorical variables and means and standard deviations or medians and interquartile ranges for continuous outcomes) will be used to compare baseline demographic, physiologic and clinical

outcomes between the two treatment groups. All statistical tests are two-sided with alpha = 0.05.

Analysis of Primary Outcome (NICU Admission)

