The primary endpoint to be used for efficacy evaluation is the rate of NICU admission (by predefined criteria). The primary hypothesis to be tested is whether the UCM group's results show a lower event rate compared to the ECC group. The primary analysis will estimate relative risks and 95% confidence intervals, accounting for the cluster randomized crossover study design, with fixed or random effects for treatment group effect, period effect, cluster effect and cluster by period interaction effect. The analysis will also account for multiple gestations and clustering within a pregnancy if more than one neonate of a multi-gestation pregnancy meets eligibility. If the treatment groups are found to differ on a pre-treatment factor known to be a risk factor for the outcome, the statistical analysis will adjust for these differences. An evaluation of treatment by site interaction will be included. The percent of patients missing information to define the primary outcome is expected to near 0%. Death is not an anticipated competing risk for the primary outcome as it is expected that all randomized newborns requiring NICU admission will be admitted immediately. However, a sensitivity analysis will be conducted using a composite outcome of NICU admission (by predefined criteria) or death.

Subgroup analyses should be pre-specified and interpreted with care. Prior studies offer no basis for assuming a priori interactions between treatment groups, strata and subgroups defined by sex, race/ethnicity, gestational age, site or a combination of these groups, beyond that already controlled for in the randomization. For these reasons, preplanned tests for interactions with treatment assignment are not warranted and are not powered for with the sample size. However, in accordance with NIH guidelines, an evaluation of consistency across racial/ethnic subgroups will be included.

Analysis of Secondary Outcomes

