Secondary outcomes (use of therapeutic hypothermia, use of volume expanders, hemoglobin, bilirubin, death, and neurodevelopmental follow up scores) will be analyzed using similar multivariable procedures accounting for the study design as for the primary outcome to test treatment effects. Analyses will estimate relative risks and 95% confidence intervals for binary outcomes and means or mean differences and 95% confidence intervals for continuous outcomes. Secondary outcomes will be evaluated for missing data and those with and without missing data will be compared. Multiple imputation analysis will be conducted as warranted. Analyses will also evaluate death as a competing risk. No adjustment for multiple comparisons of secondary outcomes is planned.

Exploratory Analyses

Several outcomes are identified as exploratory (level of HIE, blood pressure, length of hospitalization, resuscitation interventions, and placental pathology). These analyses will focus on descriptive statistics rather than hypothesis testing. Likewise any evaluations of subgroup differences by treatment group (other than race/ethnicity as mentioned previously) will be explored in secondary analyses for descriptive purposes and solely for purposes of generating hypotheses for future studies.

Follow up Study- While all secondary and exploratory outcomes that occur during the delivery hospitalization will be presented in the primary paper, all subjects will continue to be followed until 24 months of age to determine their long-term outcome. The sample size is powered to detect differences in their Ages and Stages Composite and MCHAT scores.

Substudies for cerebral oxygenation and echocardiography will be reported as separate projects on clinical trials.gov and analyzed independently.

VI. Recruitment

Eligibility criteria

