The eligibility will be determined for each child at birth. Any vigorous or crying infant will receive usual care and will not be included in the study. All high-risk deliveries attended by the Pediatric team will be screened. If the infant is determined to be non-vigorous and needs resuscitation, the baby receives the treatment arm as assigned per the trial and will be added to the screening log as eligible for follow up. If the infant did not meet any exclusion criteria, the site's designated research coordinator or their designee will approach parents following delivery and resuscitation to explain the remaining portion of the study (ongoing data collection, and periodic contact via phone, text, letter or email for developmental follow-up studies). Each site will be responsible for maintaining their own master screening log. The purpose is for each screened patient to be assigned a study number to track eligibility, informed consent and data collection. The log with the study numbers and site patient identifiers will be kept in a secure, limited access area at each center. Only investigators and research personnel who are involved with the study will have access to the site specific log.

Inclusion Criteria

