As a pragmatic trial, all deliveries that do not meet exclusion criteria will be included. We acknowledge that anticipating resuscitation based on fetal (abnormal fetal heart rate tracing) or delivery (need for instrumentation or meconium) criteria do not accurately predict the need for resuscitation. The determination for eligibility will be determined for each child at birth by the obstetrical provider. Any vigorous or crying infant will receive usual care (i.e., delayed cord clamping) and will not be included in the study. If the infant is non-vigorous as determined by usual practice the baby receives the treatment arm as assigned per the trial. **Non-viable infants or infants of unknown viability will not be included in the trial, only viable infants in distress. Infants born in extremis for whom no additional treatment will be offered by the attending neonatologist will not be enrolled in this trial. The individuals making the assessment of the infant at birth (Obstetrical Residents, Obstetrician, Midwife or other perinatal provider) are not co-investigators or key personnel so they will have no conflict of interest regarding enrollment.** Based on annual deliveries and the number of infants with a low Apgar score ≤ 3 , we anticipate this will occur in about 3 percent of all term/near-term deliveries at each site.

- Non-vigorous Infants delivered at 35-41+6 weeks GA

Exclusion Criteria

- Known major congenital or chromosomal anomalies of newborn
- Known cardiac defects other than small ASD, VSD and PDA
- Complete placental abruption/cutting through the placenta at time of delivery
- Monochorionic multiples
- Cord anomaly (i.e. cord avulsion, true knot)
- Presence of non-reducible nuchal cord
- Perinatal providers unaware of the protocol

- Incomplete delivery data
- Infants born in extremis, for whom additional treatment will not be offered

This protocol will not adversely affect the rights and welfare of subjects, and will involve no more than minimal risk to subjects. This study meets the criteria of 45 CFR 46 Subpart D a) 404 the research is not greater than minimal risk.

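### The undefined exclusion for incomplete delivery data can be judged only after treatment, yet as written it removes treated infants from the primary analysis

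*Combined protocol and SAP*

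**What the plan says.** - The Protocol Summary and Section VI (Exclusion Criteria) both list "Incomplete delivery data" as an exclusion. Neither defines it or says which items must be present.
- Section VI (Eligibility criteria) states: "The eligibility will be determined for each child at birth".
- Section IV (Maintaining Adherence to Algorithms) analyses protocol violations by original allocation, then adds: "Only newborns who meet pre-defined exclusion criteria (i.e. cord avulsion or congenital anomaly) will be excluded from the primary analyses". The sentence continues with a safeguard: "we will verify that there is not a differential occurrence by treatment from procedure".
- Section V (Statistical Approaches for Testing Hypotheses) states: "All statistical analyses will be based upon the total cohort of patients randomized into the trial". It specifies intention to treat.
- Section V (Analysis of Primary Outcome) states: "The percent of patients missing information to define the primary outcome is expected to near 0" per cent. It gives no missing-data method for that outcome. The method is under secondary outcomes: "Secondary outcomes will be evaluated for missing data and those with and without missing data will be compared".
- The Appendix 3 delivery room form records the treatment received, number of milkings, clamping time, respiratory support and disposition.
- Section IX (Data Collection) and Appendix 1 place disposition in the minimal data set taken under waiver for all eligible infants, apart from those whose parents opt out.
- The screening log described in Section VII (Waiver of HIPAA Authorization) holds NICU admission and the reason an infant was not enrolled.

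**The concern.** An exclusion criterion should be a fact about the infant or delivery that exists before treatment. Completeness of the delivery record is a property of documentation, and much of what is documented happens at or after the cord treatment. Used as an exclusion, it turns missing data into ineligibility.

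The trial is unblinded, and the delivery form carries the assigned arm at the top and the disposition at the bottom. A decision that a record is incomplete can therefore be made with arm and outcome in view. If removal is related to arm and to NICU admission, the primary relative risk is biased and the analysis is no longer by intention to treat for those infants.

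The loss is also unnecessary. The arm follows from hospital and epoch, and NICU admission is available outside the form.

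**Working it through.** **1. Reading the sections together.** The criterion is an exclusion (Protocol Summary, Section VI). Its status is known only after treatment (Appendix 3). Infants meeting an exclusion leave the primary analyses (Section IV). Eligibility is settled at birth (Section VI), and all randomized patients are analysed by intention to treat (Section V). The first three statements cannot be followed together with the last two.

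**2. The plan's own figure.** Inputs from Section V: 25% versus 16.25%, two-sided alpha 0.05, 85% power, rho = eta = 0.02, and a correction of 4 × cluster size. With 1200 infants, ten sites and two periods, cluster-period size m = 1200/20 = 60.

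- Two-proportion sample size: 383 per arm.
- Design effect: 1 + 59 × 0.02 − 60 × 0.02 = 0.98, so 383 × 0.98 = 375.3.
- Adding 4 × 60 = 240 gives 615.3 per arm, or 1231 in total.

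This is within 3% of 1200, so the sample size is not in dispute. On the same method, power at 1200 is 83.6%. It falls to 81.6% if 5% of infants are removed and 79.5% if 10% are. Power is the lesser cost.

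**3. Bias under assumed removal rates.** The documents give no rate of incomplete data, so everything in this step is illustration. Let p be the true admission rate in an arm, r the fraction removed and q the admission rate among those removed:

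observed rate = (p − r·q) / (1 − r)

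Assumptions: r = 5% in UCM and 1% or 2% in ECC; q = 40% or 60% in ECC. Three cases:

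- Case A, no true effect: p = 25% in both arms, same q in both.
- Case B, planned effect, also present in removed infants: p = 16.25% in UCM, UCM q = 0.65 × ECC q (26% or 39%).
- Case C, planned effect overall, but none in removed infants: p = 16.25% in UCM, same q in both arms.

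Example, ECC 1% removed, q = 60%:

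- ECC = (0.25 − 0.01 × 0.60)/0.99 = 24.65%.
- UCM, A = (0.25 − 0.05 × 0.60)/0.95 = 23.16%.
- UCM, B = (0.1625 − 0.05 × 0.39)/0.95 = 15.05%.
- UCM, C = (0.1625 − 0.05 × 0.60)/0.95 = 13.95%.

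| ECC removed | ECC q | ECC observed | UCM, A | RR, A | UCM, B | RR, B | UCM, C | RR, C |
|---|---|---|---|---|---|---|---|---|
| 1% | 40% | 24.85% | 24.21% | 0.974 | 15.74% | 0.633 | 15.00% | 0.604 |
| 1% | 60% | 24.65% | 23.16% | 0.940 | 15.05% | 0.611 | 13.95% | 0.566 |
| 2% | 40% | 24.69% | 24.21% | 0.980 | 15.74% | 0.637 | 15.00% | 0.607 |
| 2% | 60% | 24.29% | 23.16% | 0.954 | 15.05% | 0.620 | 13.95% | 0.574 |

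Against the target difference of 8.75 points, the observed difference grows by 0.2-0.8 points in case B and 0.9-2.0 points in case C. If ECC records are the less complete (5% ECC, 1-2% UCM), the null relative risks invert to 1/0.980 to 1/0.940, or 1.02-1.06.

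**4. Type I error.** With 2% of ECC and 5% of UCM infants removed and a true null, two-sided type I error is about 6% if half the removed infants were admitted and about 10% if three quarters were. This uses a normal approximation with design effect 0.98 and no small-cluster correction.

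**5. What a comparison of counts would miss.** Suppose 5% are removed in both arms, with 40% of removed ECC infants and 60% of removed UCM infants admitted, under a true null. The relative risk is (0.25 − 0.03)/(0.25 − 0.02) = 0.22/0.23 = 0.957, although the counts match exactly. If removal fractions and admission rates are both equal across arms, there is no bias under the null.

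**The case against.** **The safeguard.** Section IV does promise to verify that exclusions do not differ by treatment, and differential removal drives the illustration in step 3. This must be credited, but it names no method, threshold or action. It restores no infant, and a comparison of counts would not show whether removed infants were sicker in one arm.

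**The inference.** Section IV's examples are cord avulsion and congenital anomaly. Removal for incomplete data follows from its general wording and is not named there. Nor do the documents say that a late or partly filled Appendix 3 form is what the criterion means. This is fair, and it is why the point is about an undefined term applied through a general rule.

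**A legitimate purpose.** Inclusion rests on provider judgement, with tone, colour and breathing as the agreed recorded reasons. The criterion may be meant for infants whose non-vigorous status cannot be verified. The text does not say so, but the fix should allow for it.

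**Readings that go too far.** A reader might infer that the exclusion makes the near-zero missing-outcome figure true by construction. It does not: NICU admission is available outside the delivery form, so removing infants with incomplete delivery data need have little effect on outcome missingness. A reader might also infer that no analysis could reveal the problem. The screening log keeps removed infants, with NICU admission and reason for non-enrolment, so it can be examined. Finally, one might assume that incomplete records cluster in the sickest infants, or in UCM epochs because the number of milkings must be entered. The documents give no evidence for the first, and both arms use one form.

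**Conclusion.** The conflict is in the text. As written, a post-treatment, undefined data-completeness criterion can remove treated infants from the primary analysis of an unblinded trial that otherwise commits to eligibility at birth and total-cohort intention to treat.

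The size and direction of any bias are unknown. Under the assumed rates, a null effect appears as 0.94-0.98, and the planned 0.65 as about 0.61-0.64 or 0.57-0.61, depending on whether UCM works in the removed infants. The larger shift should not be read as the expected one, because it requires UCM to have no effect in exactly those infants. Nor do the documents support concluding that the bias favours UCM; it reverses if ECC records are the less complete.

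Severity: should fix. The rule governs who enters the primary analysis and is cheap to correct, but a material effect has not been shown.

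**What to change.** 1. In the Protocol Summary and Section VI, stop using incomplete delivery data as a reason for removal from the primary analysis.
2. Keep every infant logged as non-vigorous at 35+0 to 41+6 weeks who meets no other exclusion criterion and whose parents did not opt out, under the arm assigned to that hospital and epoch.
3. Take NICU admission from the minimal data set and medical record collected under waiver (Sections VII and IX, Appendix 1).
4. Treat missing delivery-room items as missing covariate or process data, and report incomplete records by arm and epoch.
5. Restore infants already removed under this criterion, using the screening log.
6. If non-vigorous status cannot be confirmed from any record, report those infants by arm and include them in a sensitivity analysis.

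The cost is amendment wording and retrieval of NICU status for infants already logged as incomplete. No new patients or procedures are needed. Some analysed infants will lack descriptive items.

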Umbilical cord milking consists of gently grasping the uncut umbilical cord and squeezing the cord from the placenta several times toward the infant. The available studies on cord milking for vigorous term infants, when compared to Early Cord Clamping (ECC), include one systematic review five RCTs (15-17, 27) and five older controlled trials (13, 28-31). These studies conclude that cord milking significantly improves blood pressure, hematocrit, and hemoglobin levels within the first few days of life and iron stores out to 6 months of age, with no associated harm. In late preterm infants, higher ferritin levels at 6 weeks of age are reported after UCM (32). None of the studies demonstrated harm from UCM in these vulnerable infants, but also have not shown any clinical benefit. A recent study (PREMOD2) was stopped due to increased severe IVH in infants receiving UCM less than 28 weeks gestation compared to delayed cord clamping. There were no differences in death, or total IVH between the two groups.

Cord milking in the most immature infants may be inferior to delayed cord clamping where a vascularized germinal matrix may be prone to bleeding with cord milking.

[figure not shown]

Figure 1

Physiology of Umbilical Cord Milking.

UCM provides a replacement preload before removing the placenta from the circulation, increasing pulmonary and cerebral circulation, and thus may mitigate further ischemia to an already compromised infant. Successful transition for non-vigorous infants may require active transfer of blood directed towards the pulmonary circuit by UCM. (see **Figure 1**, courtesy [name]) Increased pulmonary blood flow has been shown with recordings of electrocardiographic changes—vigorous newborns that had UCM had a longer P wave, PR, and QTC interval when compared with those who had early cord clamping (28). UCM may enhance alveolar patency compared to DCC or ECC by improving pulmonary capillary blood flow (33). Our recently completed retrospective study of term/near-term newborns with acidemia at birth suggested **decreased need for resuscitation, and ongoing respiratory support** after UCM compared to ECC (34). Whether a similar benefit will result from UCM in non-vigorous term/near-term infants is unknown. Based on currently available literature there is no foreseeable risk to the baby or to the mother with either ECC or UCM.

Are OB Providers Using Cord Milking?

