As with any study, there may be risks that currently are unforeseeable.

Risk Management

Protection against Risk

Practitioners at all sites have experience with performing UCM and ECC within their normal clinical care. Only research team members (with appropriate research training relevant to protection of human subjects) shall have access to the project's databases.

Management of Risks

Hemoglobin lab draw: Will be performed by clinical staff that are trained and experienced in drawing blood from newborns. Proper techniques will be used at all times to minimize the chance of infection thereby minimizing potential risks related to the collection of blood samples. All efforts will be made to reduce infants discomfort (i.e. warming infants heel, providing oral glucose, or hospital standard practice).

Data Collection and Survey Completion

All data will be safeguarded in accordance with the Health Insurance Portability and Accountability Act (HIPAA) and the principles and practices of strict confidentiality. Every reasonable effort will be made to keep the subjects records confidential. Subject's records will be stored in a secure office. Codes, instead of names, will be used to identify the collected information.

Reporting Process

The population being studied is at increased risk of all complications (such as hypoxic ischemic encephalopathy) associated with term and near-term infants who are deemed to require immediate resuscitation. The majority of these events will be expected and included in data collection and reported in all DSMB analyses. However, all SAE's of death, polycythemia/jaundice requiring exchange transfusion, pulmonary hemorrhage and severe IVH (grade 3 or 4) on HUS or MRI will be reported within 3 days of discovery of event, to UCSD DCoC via REDCap.

Monitoring

The DCoC will send out monthly reports detailing enrollment, SAE's, protocol deviations and data queries. Clinical Coordinating Center (SMBHWN) Data team will be monitoring sites as needed throughout the trial. The purposes of monitoring visits, which will generally be done by phone or GoToMeeting, are to:

- Ensure the rights and safety of participants
- Confirm that the study is conducted in accordance with GCP guidelines
- Ensure maintenance of required documents
- Verify adherence to the protocol
- Monitor the quality of data collected
- Ensure accurate reporting and documentation of all AEs and unanticipated problems

Data Safety Monitoring Board (DSMB)

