An expert board consisting of perinatologists, neonatologists, outside statisticians and a former NICU parent will be closely reviewing all serious adverse outcomes. This group has been established to: 1) protect all study patients, 2) safeguard the interests of all study patients, 3) monitor the overall conduct of the trial, 4) advise the investigators to protect the integrity of the trial, and 5) supervise the conduct and analysis of all interim analyses. The DSMB will review the first 200 enrolled infants. If the first review does not show any evidence of safety signal for adverse outcomes in either group on blinded analyses, additional blinded reviews will be conducted when 50 and 75 percent of subjects are enrolled. If the odds ratio of NICU admission or death between the two arms exceeds a threshold, it will trigger a safety signal. We will suggest to the DSMB the threshold of an odds ratio of 2.5 as the threshold for a formal meeting to discuss potentially stopping the trial. However, the DSMB should discuss and determine the threshold. There is no plan to stop for efficacy as the trial design (cluster randomized cross-over) necessitates that both arms of the trial be completed at each site before efficacy can be

adequately assessed. If the trial were stopped prematurely, we would perform planned analyses on the data collected at the time of the closing of the study. The findings will be communicated to all study staff by the data center in monthly reports via email. According to the study's Statistical Analysis Plan and due to the cross-over design of the study, there will be no planned formal interim analysis for efficacy or futility.

IX. Data Management

Centralized Data Collection

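### The only stated numerical safety trigger, an odds ratio on NICU admission or death, is insensitive to excess deaths among admitted infants and leaves out the three non-fatal SAEs

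*Combined protocol and SAP*

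**What the plan says.** All references are to the combined protocol and SAP.

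- **Section VIII, Data Safety Monitoring Board.** The trigger reads: "If the odds ratio of NICU admission or death between the two arms exceeds a threshold, it will trigger a safety signal". The value is a proposal: "We will suggest to the DSMB the threshold of an odds ratio of 2.5 as the threshold for a formal meeting", followed by "However, the DSMB should discuss and determine the threshold". On timing: "The DSMB will review the first 200 enrolled infants". Then: "If the first review does not show any evidence of safety signal for adverse outcomes in either group on blinded analyses, additional blinded reviews will" follow at 50 and 75 percent of enrolment. There is no efficacy or futility stopping.
- **Section V, Analysis of Primary Outcome.** NICU admission by the predefined criteria, or death, is named as a composite outcome for a sensitivity analysis. Death is not treated as a competing risk because "it is expected that all randomized newborns requiring NICU admission will be admitted immediately".
- **Section VIII, Reporting Process** (repeated in section IX). The events that sites must report within 3 days are "all SAE's of death, polycythemia/jaundice requiring exchange transfusion, pulmonary hemorrhage and severe IVH (grade 3 or 4) on HUS or MRI". The coordinating center forwards each report to the DSMB.
- **Section IX, Data Safety Monitoring Board.** The DSMB also receives monthly adverse event reports, and the text mentions stopping rules fixed in advance. No such rule or figure is given there.

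**The concern.** A trigger for a formal meeting on stopping should respond to the harms that would justify stopping. This one is dominated by admissions, which the plan expects in a quarter of ECC infants. An infant who is admitted and later dies is already an event on the day of admission. A non-fatal SAE in an admitted infant changes nothing either. If UCM lowers admissions, as the trial hypothesises, the composite could favour UCM while deaths rise.

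This matters because infants are treated under a waiver of antenatal consent that rests on minimal risk, so monitoring is a main safeguard. The protocol makes severe IVH a 3-day SAE, yet states no rule for comparing its rate between arms.

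The timing wording adds a smaller gap. The 50% and 75% reviews are written as following a first review without a signal, so the text does not say what is scheduled if a signal appears and the trial continues.

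**Working it through.** **Plan's own figure.** The value 2.5 comes with no derivation, so there is nothing to reproduce. The admission rates are consistent with the stated 35% reduction: 1 − 16.25/25 = 0.35.

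**Inputs from the documents.** Admission 25% (ECC) and 16.25% (UCM); threshold 2.5; N = 1200; reviews at 200, 600 (50%) and 900 (75%) infants.

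**Assumptions.** Equal arms (100, 300 and 450 per arm at the reviews), no clustering, and the death and IVH rates shown, since the documents give none.

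**Formula.** OR = [p1/(1 − p1)] / [p0/(1 − p0)], with UCM as p1 and ECC as p0.

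**Step 1: what it takes to exceed 2.5.** With p0 = 0.25 the ECC odds are 1/3. The UCM rate must exceed (2.5/3)/(1 + 2.5/3) = 45.5%, an excess of 20.5 points. In counts:

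| Review | ECC events | Smallest UCM count with OR > 2.5 | Excess |
|---|---|---|---|
| 200 infants | 25/100 | 46/100 | 21 |
| 600 infants | 75/300 | 137/300 | 62 |
| 900 infants | 112/450 | 204/450 | 92 |

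Check on the first row: (46/54)/(25/75) = 2.56, while 45 events give 2.45. If the ECC rate is anywhere from 16.25% to 60%, the UCM rate needed is 32.7% to 78.9%.

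**Step 2: how far deaths move the composite, with 25% admission in both arms.**

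- All deaths after a counted admission: 0.25 versus 0.25, OR = 1.00 whatever the mortality difference.
- All deaths before admission, 1% versus 3%: 0.28 versus 0.26, OR = 1.11.
- All deaths before admission, 1% versus 5%: 0.30 versus 0.26, OR = 1.22.
- The same 1% versus 5%, with UCM admissions at 16.25%: 0.2125 versus 0.26, OR = 0.77.

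**Step 3: a larger excess, 2% versus 10% mortality.** The OR for death alone is (0.10/0.90)/(0.02/0.98) = 5.4. Fisher's exact p is 0.033 for 10 versus 2 deaths per 100, and 0.00004 for 30 versus 6 per 300. Holding the ECC composite at 25%, and computing crossing probabilities by exact binomial enumeration:

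- All deaths after admission, equal admission rates: OR 1.00. The chance of crossing 2.5 is 0.4% at 200 infants and about 0 at 600 and 900.
- Every excess death in a non-admitted infant: 0.33 versus 0.25, OR 1.48. The chance is about 5.5% at 200 infants and 0.2% at 600.
- Even 2% versus 20%, every excess death in a non-admitted infant: 0.43 versus 0.25, OR 2.26.

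**Step 4: a non-fatal SAE.** Severe IVH at an assumed 1% versus 10% has its own OR of (0.10/0.90)/(0.01/0.99) = 11.0. In infants already admitted it adds nothing to the trigger.

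**Step 5: the other reading, separate odds ratios for admission and for death.** Deaths of 1% versus 3% then give 3.06, and 1% versus 5% give 5.21; both exceed 2.5. At 2% versus 10% the rule is crossed with probability 88%, 98% and 99% at the three reviews. With equal 2% mortality it is still crossed by chance with probability 22%, 8% and 4%. These figures count only an apparent excess under UCM, and treat any UCM death against none under ECC as a crossing.

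**The case against.** **The threshold is not the only route to a meeting.** A reader might infer that a large excess of deaths or severe IVH would pass without any stopping meeting. The documents do not support that. The DSMB is to review all serious adverse outcomes, its first review looks for a signal in either group, every SAE report is forwarded to it, and adverse event reports come monthly. What stands against the plan is narrower: nothing stated makes such an excess call the meeting automatically.

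**Death is in the trigger.** A reader might also infer that the SAEs are wholly outside it. Death is both a listed SAE and a component; only the three non-fatal SAEs are absent. A death without admission does move the ratio. So would a death after an admission for a non-listed reason, if the Appendix 2 criteria govern the trigger.

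**The value is only suggested, and a charter may hold more.** The board sets the threshold, and section IX refers to stopping rules that the documents do not show. This limits what can be said about the rules in force. But the text hands over the threshold, not expressly the endpoint, and no choice of threshold repairs a ratio that stays at 1.00 under excess mortality.

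**The wording may mean separate ratios.** That is possible: the DSMB section does not use the word composite. But it speaks of one odds ratio, and section V treats the same pair as a composite. If separate ratios are meant, the text should say so. The rule would then be noisy for rare deaths (step 5) and would still omit the non-fatal SAEs.

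**The IVH precedent is distant.** The background says "A recent study (PREMOD2) was stopped due to increased severe IVH in infants receiving UCM less than 28 weeks gestation"; the comparison there was with delayed clamping, with no difference in death or total IVH. It does not show a risk at 35 weeks or later against early clamping, and this point does not depend on it. That the protocol itself lists severe IVH as an SAE is enough.

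**Conclusion.** The point holds as a gap in the stated monitoring rule and should be fixed. Under the composite reading, which section V supports, the only numerical trigger cannot register deaths after a counted admission and does not cover exchange transfusion, pulmonary hemorrhage or severe IVH. Even if every death preceded admission, a fivefold mortality ratio (1% versus 5%) would leave the odds ratio far below 2.5.

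The size rests on assumed death rates, equal arms, no clustering and an ECC composite near 25%. The insensitivity to deaths after a counted admission does not depend on the death rates chosen. The finding does not show that the DSMB would miss such harm, only that the written threshold would not bring it to a formal meeting. The primary analysis is unaffected.

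**What to change.** In section VIII, Data Safety Monitoring Board, and in the DSMB charter:

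1. State that the trigger is a composite of NICU admission or death, say whether the Appendix 2 criteria apply to it, and keep it.
2. At every review add two by-arm comparisons, each with its own trigger for a formal meeting: death from any cause, and infants with any other SAE listed under Reporting Process.
3. Use a rule suited to rare events, for example an exact comparison for harm in either arm, which can be run with masked arm labels. The DSMB should fix its level before the next review.
4. Note that comparisons made before crossover are largely between hospitals and must be read with caution because of clustering.
5. State that the 50% and 75% reviews are held whatever the first review shows, if the trial continues.

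The cost is wording and two more lines in each DSMB report, from SAE data already sent to the coordinating center. The downside is a few more meetings called by chance.
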